### **9.5.3 Analyses of Exploratory Efficacy Endpoint(s)**

#### **9.5.3.1 Exploratory – Part A and Part B**

The exploratory endpoints for Part A and Part B per [Section 5.6](#) will be analyzed separately.

##### ***Part A***

For binary endpoints, IGA 0/1, EASI 75, EASI 50/90, each at week 24, week 36 and week 52, the treatment effect will be analyzed using a logistic regression model adjusting for corresponding baseline values as covariates. From each model, odds ratio and 95% CIs will be reported comparing each tezepelumab dose group to placebo.

SCORAD, DLQI, Pruritus NRS, POEM, and PGI-S scores and changes from baseline will be summarized by visit. Absolute improvement and percent improvement will be summarized for the EQ-5D TTO score. In addition, absolute and percent improvement will be calculated for each of the five EQ-5D-3L attributes individually. The EQ VAS score will be summarized.

For continuous endpoints, change from baseline in each of IGA, EASI, SCORAD, Pruritus NRS, PGI-S, POEM, and DLQI at week 24, week 36 and week 52, the treatment effect will be analyzed using the MMRM models with visit and corresponding baseline scores as covariates and an interaction term between arm

and visit. AR(1) variance-covariance structure will be used. Least square means and corresponding 95% CI will be calculated for each treatment group and for the difference between treatment groups. Efficacy data collected after switching to 420 mg SC Q2W point will be truncated.

The MMRM models will be repeated using the Switcher Analysis Set only, utilizing all available observations for subjects in the set. For binary outcomes of IGA 0/1 and EASI 75 at week 24, week 36 and week 52, descriptive summary of response rates will be provided by randomized treatment arm for the Switcher Analysis Set. For continuous outcomes of IGA, EASI, SCORAD, Pruritus NRS, PGI-S, POEM, and DLQI change from Baseline will be summarized descriptively by randomized treatment arm for the Switcher Analysis Set.

Biomarker analysis, if performed, will be detailed in [Section 9.7.4](#).

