7.1.5 Other Treatment Procedures

During the 28-day screening period, subjects must discontinue from all AD therapies, except for approved moisturizers (see [Section 7.1.7](#)), for at least the 7 consecutive days immediately prior to day 1. During the study, approved moisturizers are allowed to be applied, with the exception of 8 hours prior to any scheduled visit.

Medications and procedures permitted at any time during the study for subjects enrolled in Part A and Part B include:

- Basic skin care (cleansing and bathing), emollients, bleach baths, topical anesthetics, and antihistamines (all for any duration)
- Medications used to treat chronic diseases such as diabetes, hypertension, and asthma

Part A

In Part A of the study, if needed to control intolerable AD symptoms, rescue treatment for AD may be provided at the discretion of the investigator. Rescue is not allowed in the first 4 weeks of Part A. Topical calcineurin inhibitors may be used for rescue, but are to be reserved for problem areas only (eg, face, neck, intertriginous and genital areas). Investigators are to attempt to limit the first step of rescue therapy to topical medications, and escalate to systemic medications only for subjects who do not respond adequately following at least 7 days of topical treatment. If a subject receives rescue treatment with systemic corticosteroids or nonsteroidal systemic immunosuppressive drugs

(eg, cyclosporine, mycophenolate-mofetil, azathioprine), study treatment is to be immediately discontinued.

All subjects are to complete the schedule of study visits and assessments whether or not they complete study treatment or receive rescue treatment for AD.

Part A Rescue Guidance

Subjects who use TCS are to apply medium potency TCS once daily to areas with active lesions. Low potency TCS should be used once daily on areas of thin skin (eg, face, neck, intertriginous, genital areas, areas of skin atrophy) or for areas where continued treatment with medium potency TCS is considered unsafe.

Triamcinolone acetonide 0.1% cream or fluocinolone acetonide 0.025% ointment are recommended as medium potency TCS therapy; hydrocortisone 1% cream is recommended as low potency TCS therapy. After lesions are under control (clear or almost clear), subjects are to switch from medium potency to low potency TCS and treat once daily for 7 days, then cease TCS therapy.

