## 5.4 Study Endpoints

### Investigator's Global Assessment (IGA)

The IGA allows investigators to assess overall disease severity at 1 given time point and consists of a 6-point severity scale from clear to severe disease (0 = clear; 1 = almost clear; 2 = mild disease; 3 = moderate disease; 4 = severe disease; 5 = very severe disease). The IGA uses clinical characteristics of erythema, infiltration, papulation, oozing, and crusting as guidelines for the overall severity assessment ([Breuer et al, 2004](#)).

**For subjects who take rescue medication of TCS/TCI from day 29, their IGA score will be ignored on and after the date of rescue medication.**

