### Eczema Area and Severity Index (EASI)

The EASI is designed by modifying the Psoriasis Area and Severity Index, which has been widely used in clinical trials and has been established as a well-accepted and standardized instrument for assessing therapeutic response in patients with psoriasis ([Schmitt et al, 2007](#)). The EASI evaluates 4 natural anatomical regions for severity and extent of key disease signs and focuses on key acute and chronic signs of inflammation (ie, erythema, induration/papulation, excoriation, and lichenification). The maximum score is 72, with higher values indicating more severe disease.

For subjects who take rescue medication of TCS/TCI from day 29, their EASI score will be ignored on and after the date of rescue medication.

Body Region	Severity	Area	Score
Head/Neck (H)	The average degree of severity of each sign (erythema [E], induration/papulation [I], excoriation [EX] and lichenification [L], is defined on a 4-point ordinal scale:  0 = none 1 = mild 2 = moderate 3 = severe	The area is defined on a 7-point ordinal scale:  0 = no eruption 1 = <10% 2 = 10% - 29% 3 = 30% - 49% 4 = 50% - 69% 5 = 70% - 89% 6 = 90% - 100%	$(E+I+EX+L) * Area * 0.1$
Upper Limbs (UL)			$(E+I+EX+L) * Area * 0.2$
Trunk (T)			$(E+I+EX+L) * Area * 0.3$
Lower Limbs (LL)			$(E+I+EX+L) * Area * 0.4$
EASI Score			Sum of scores of H, UL, T, and LL

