For subjects who take rescue medication of TCS/TCl after day 29, their SCORAD score will be ignored on and after the date of rescue medication.

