## 5.5 Primary Endpoints

### IGA 0/1 at week 16

The primary endpoint, IGA 0/1 at week 16 in the absence of rescue medication of TCS/TCI from day 29 to week 16 in Part A, will be derived as follows:

- Derive IGA 0/1 at week 16 as 1, if the IGA score is 0 or 1 at week 16 and no rescue medication of TCS/TCI from day 29 to week 16
- IGA 0/1 at week 16 will be missing if there is no IGA assessment at week 16 and either no rescue medication of TCS/TCI from day 29 to week 16 or the use of rescue medication is unknown during day 29 to week 16
- Otherwise derive IGA 0/1 at week 16 as 0

### EASI 75 at week 16

The primary endpoint, EASI 75 at week 16 in Part A, will be derived as follows

- Derive EASI 75 at week 16 as 1, if there is greater than or equal to 75% improvement in EASI score from baseline and no rescue medication of TCS/TCI from day 29 to week 16
- EASI 75 at week 16 will be missing if there is no EASI assessment at week 16 and either no rescue medication of TCS/TCI from day 29 to week 16 or the use of rescue medication is unknown during day 29 to week 16
- Otherwise derive EASI 75 at week 16 as 0.

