## 5.6 Secondary/Exploratory Endpoints – IGA 0/1 and EASI 50/75/90

Secondary endpoints, EASI 50 and EASI 90 at week 16 in Part A, and Exploratory endpoints, IGA 0/1 at week 24, week 36 and week 52 in Part A and B, and IGA 0/1 at week 16 in Part B, will be defined in the same way as primary endpoints in [Section 5.5](#). For example, the time point of interest is week 24, week 36 and week 52 instead of week 16, the use of TCS/TCI will be considered from day 29, to week 24, week 36 and week 52 respectively.

Time-to-event analysis of EASI 50/75/90 will be handled as described in [Section 9.5.2](#) and [Section 9.5.3](#).

In addition, IGA 0/1 and EASI 75 at time points other than week 16, week 24, week 36 and week 52 in both Part A and B will be defined in the same way as primary endpoints in [Section 5.5](#) at corresponding time points. For example, when the time point of interest is week 4, week 6, week 8, week 10, and week 12 instead of week 16, the use of TCS/TCI will be considered from day 29, to those time points respectively.

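### In the visible SAP text the day-29 rescue rule is not restarted at the switch, so topical rescue on the randomised regimen fixes a switcher as an IGA 0/1 non-responder through week 52

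*SAP*

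**What the plan says.** **Scores (SAP 5.4).** Once a subject takes TCS/TCI rescue from day 29, for IGA "their IGA score will be ignored on and after the date of rescue medication", and for EASI "their EASI score will be ignored on and after the date of rescue medication". For SCORAD, "their SCORAD score will be ignored on and after the date of rescue medication"; pruritus NRS, POEM, PGI-S, DLQI and EQ-5D have the same rule. (These six say after day 29 where IGA and EASI say from day 29.) None of the eight entries gives an end to the rule.

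**Responder endpoints (SAP 5.5 and 5.6).** A response at week 16 needs the score and no TCS/TCI from day 29. The endpoint is missing only if there is no assessment and rescue is absent or unknown. Everything else falls to the last branch: "Otherwise derive IGA 0/1 at week 16 as 0". SAP 5.6 carries this derivation to IGA 0/1 at the later visits, where "the use of TCS/TCI will be considered from day 29, to week 24, week 36 and week 52 respectively". It names EASI 75 only in a sentence on "IGA 0/1 and EASI 75 at time points other than week 16, week 24, week 36 and week 52".

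**Switchers.** SAP 5.2 defines a Switching Date, the first 420 mg Q2W dose after week 16 in a week 16 non-responder. SAP 9.5.3.1 then says "The MMRM models will be repeated using the Switcher Analysis Set only, utilizing all available observations for subjects in the set", and adds descriptive IGA 0/1 and EASI 75 rates at weeks 24, 36 and 52 by randomised arm.

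**Rescue in practice.** Protocol 7.4.2.1 lets subjects with topical rescue stay on study drug. The Part A guidance in Protocol 7.1.5 is to step down once lesions are controlled: "treat once daily for 7 days, then cease TCS therapy".

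**The concern.** The SAP otherwise treats the switch as a break. FAS efficacy data are truncated there (9.5, 9.5.3.1), time to EASI response is taken before it (9.5.2), and actual treatment and the safety windows are divided there (5.1, 9.6). The rescue rule is the exception.

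Consider a placebo subject who uses TCS in week 8, steps down and stops, is below EASI 50 at week 16, switches, and is clear at week 52 after months without topical treatment. The rescue took place on placebo, yet it settles this subject's IGA 0/1 result at every visit on 420 mg.

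The Switcher Analysis Set is where the plan looks at response to 420 mg after an inadequate response on the randomised regimen. If earlier rescue decides part of that result, the summaries mix two questions: how subjects did before the switch and how they did after it. Because the rates are shown by randomised arm, arms that differ in pre-switch rescue would look different even if response to 420 mg were the same.

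**Working it through.** The plan states no figure on this point, so there is none to reproduce. The check traces the rules and then sizes the effect under stated assumptions.

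**Step 1. IGA 0/1.** Take a switcher with known TCS use between day 29 and the switch, and IGA 0 at week 52.
- Response branch (5.5, with the 5.6 window): fails, because there was TCS/TCI between day 29 and week 52.
- Missing branch: does not apply, because rescue is known.
- Last branch: the endpoint is 0, and likewise at weeks 24 and 36.

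This is a derived non-response, not a missing value, so the observed-case rule for descriptive summaries in SAP 8.3.2 does not remove it. The exposed period is week 4 to week 18, that is 18 − 4 = 14 weeks. Use before day 29 does not trigger the rule; use between week 16 and the switch does.

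**Step 2. EASI 75.** The heading of 5.6 covers EASI 75, and 9.5.3.1 refers to 5.6 for the exploratory endpoints, so 0 is the natural reading. It is not stated for weeks 24, 36 and 52. If the derivation were not carried over, the ignored EASI would be missing and the subject would leave the denominator.

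**Step 3. Continuous scores.** Under 5.4 all post-switch values of this subject are ignored. SAP 8.3.2 does not impute continuous endpoints, so they are missing and the MMRM uses only pre-rescue values. The switcher sentence in 9.5.3.1 instead calls for every observation. It may lift only the truncation at the switch stated just before it, or 5.4 as well. The SAP does not say.

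**Step 4. Size (assumptions only).** Let p be the post-switch response rate in switchers without earlier rescue, and r the share of switchers with TCS/TCI between day 29 and the switch. Ignore rescue after the switch.
- Day-29 rule: reported rate = p(1 − r).
- Rescue counted from the switch, rescued switchers respond equally often: p. Gap = p × r.
- Rescue counted from the switch, rescued switchers respond half as often: p(1 − r) + (p/2)r. Gap = p × r/2.

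| p | r | Day-29 rule | From switch, equal response | From switch, half response |
|---|---|---|---|---|
| 20% | 10% | 18% | 20% | 19% |
| 20% | 30% | 14% | 20% | 17% |
| 20% | 50% | 10% | 20% | 15% |
| 40% | 10% | 36% | 40% | 38% |
| 40% | 30% | 28% | 40% | 34% |
| 40% | 50% | 20% | 40% | 30% |

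Between arms, with p = 40% in both: r = 40% gives 0.40 × 0.60 = 24%, and r = 20% gives 0.40 × 0.80 = 32%. Equal response appears as an 8-point difference.

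For EASI 75 under the missing-value reading of step 2, the observed-case rate is p(1 − r)/(1 − r) = p. That is correct if rescued switchers respond equally often. It is too high if they respond half as often: 40% against 34% at r = 30%. So the two readings of 5.6 can err in opposite directions.

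**The case against.** **The analysis-set definition is not visible.** The SAP contents list Section 6.6 for study-specific analysis sets, but that text is not available, and a restart of the rule there cannot be excluded. This limits the point to the visible text. It does not remove it: 5.6 states the day-29 window outright, and an analysis-set definition would not normally alter an endpoint derivation.

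**The rule may be intended.** Counting rescue at any time since day 29 extends the primary composite, and it is defensible as an outcome for the whole treatment sequence. The rates are shown by randomised arm rather than offered as a 420 mg estimate, and arms within a set selected on week 16 outcome are not randomised comparisons anyway. This is fair, but the SAP does not describe the switcher results as whole-sequence outcomes, and the MMRM sentence points the other way.

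**The results are exploratory.** Any p-values are nominal and the switcher response rates carry no test. This stands and limits the severity.

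Stronger readings that a reader might infer are not supported:
- That rescued switchers count as failures in the MMRM. Ignored scores are missing there.
- That all their post-switch data are certainly lost. The 9.5.3.1 sentence may override 5.4; the defect is an unresolved conflict.
- That SAP 5.6 expressly sets EASI 75 to 0 at weeks 24, 36 and 52. It does so only by implication.
- That rescued subjects are the largest or sickest part of the set. No rescue rates are given.

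**Conclusion.** The point holds for the visible SAP text. For IGA 0/1 it follows directly from 5.5 and 5.6: topical rescue between day 29 and the switch makes a switcher a non-responder at weeks 24, 36 and 52 regardless of the response on 420 mg. For EASI 75 it holds by implication. For continuous scores, 5.4 and 9.5.3.1 conflict and the SAP does not say which governs.

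The loss for IGA 0/1 is p × r if rescued switchers respond like the others: 4 to 20 points at p = 40% and 2 to 10 points at p = 20%, over r = 10% to 50%. It is half that if they respond half as often. Both p and r are assumptions, and rescue after the switch is not modelled.

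A reader might infer that the trial's main result is at risk. It is not: the week 16 primary analysis ends before the switch, and only exploratory, descriptive switcher results are affected. The change should still be made, because the rule as written gives a misleading summary and the dates needed to avoid this are already collected.

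**What to change.** 1. In SAP 5.4, 5.6 and 9.5.3.1, state that in Switcher Analysis Set analyses only TCS/TCI use on or after the Switching Date, including courses still running on that date, makes later scores ignored or the endpoint a non-response.
2. In 9.5.3.1, state that the all-observations sentence lifts the truncation at the switch and is subject to rule 1.
3. Name EASI 75 at weeks 24, 36 and 52 in 5.6.
4. Report the number of switchers with pre-switch rescue by randomised arm.
5. Leave the day-29 rule unchanged for all FAS – Part A analyses.

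The cost is a few SAP sentences and one date condition in the programs. The 5.4 change bears on eight score entries, so one general statement there is simpler than eight edits. Protocol 7.8.2 already collects start and stop dates of concomitant topical therapy. The downside is that classifying courses running at the switch depends on the stop date being recorded.

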7.4 Dose Modification

In Part A of this study, subjects who are determined to be non-responders will receive tezepelumab 420 mg SC Q2W for the remainder of the study, beginning with the week 18 dose. Non-responders are defined as those subjects who have not achieved at least a 50% improvement in EASI at week 16 compared to baseline (day 1). The randomized treatment assignments for the non-responders will remain blinded until the end of study.

In Part B, there will be no dose modification.

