### Switching Date

**If a subject is determined as non-responder at week 16 in Part A as specified by the eCRF, the Switching Date of this subject will be defined as the date that the subject takes the first dose of tezepelumab 420 mg SC Q2W after week 16 in Part A.**

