## **5.3 Baseline related definitions**

### Study Baseline

Study baseline is defined as the last non-missing measurement for the endpoint of interest taken **on or before the date of** first dose of investigational product.

**For IGA and EASI, the baseline are the IGA or EASI values collected at “Day 1” visit per protocol schedule of assessment. The values collected at “screening visit” per protocol schedule of assessment could not be used as baseline IGA or EASI.**

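### Between-arm MMRM differences among week-16 non-responders switched to 420 mg Q2W do not estimate a treatment effect and should not be reported

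*SAP*

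**What the plan says.** SAP 9.5.3.1 (Part A) models change from baseline at weeks 24, 36 and 52 in IGA, EASI, SCORAD, pruritus NRS, PGI-S, POEM and DLQI, with an arm-by-visit interaction. Its output is stated as: "Least square means and corresponding 95% CI will be calculated for each treatment group and for the difference between treatment groups". In that main model, data after the switch to 420 mg are truncated. The following paragraph adds: "The MMRM models will be repeated using the Switcher Analysis Set only, utilizing all available observations for subjects in the set". It does not limit the output to within-arm results, change the reference value or add a caveat.

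The reference is day 1. SAP 5.3 says "Study baseline is defined as the last non-missing measurement for the endpoint of interest taken" on or before the first dose, and for IGA and EASI it requires the day 1 visit.

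Protocol 7.4 defines Part A non-responders as subjects below 50% EASI improvement at week 16, and says "subjects who are determined to be non-responders will receive tezepelumab 420 mg SC Q2W for the remainder of the study", starting with the week 18 dose. This applies to every randomized arm, including the arm already on 420 mg Q2W. SAP 5.2 sets the Switching Date at "the date that the subject takes the first dose of tezepelumab 420 mg SC Q2W after week 16 in Part A".

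Binary outcomes in switchers (IGA 0/1 and EASI 75) are only summarized descriptively by randomized arm. SAP 9.5 makes any significance testing of exploratory endpoints descriptive, with nominal p-values.

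**The concern.** On its natural reading, repeating the model repeats its output, including intervals "for each treatment group and for the difference between treatment groups". In the switcher set those differences have lost both things that make them interpretable. Membership depends on a post-randomization outcome that treatment affects, so the arms are no longer comparable. After week 18 everyone is meant to be on the same regimen, so no treatment contrast remains. The 420 mg group consists of subjects who have already failed 420 mg. The placebo group consists of subjects receiving it for the first time.

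At stake is a set of point estimates with confidence intervals that would be read as dose effects, in a study whose stated purpose includes dose selection. This is also the only modelled analysis of efficacy after escalation.

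**Working it through.** The plan gives no figure for this analysis, so there is none to reproduce. The inputs taken from it are about 60 subjects per arm, 10% dropout (60 × 0.9 = 54) and EASI 75 rates of 15% (placebo) and 50% (420 mg), all from Protocol 10.1. With 54 per arm and two-sided alpha 0.025, these rates give 96.2% power for EASI 75, consistent with the stated minimum of 85%.

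The following are assumptions, not in the documents:
- the SD s of percentage EASI improvement is 25 to 50 points;
- the correlation r between the week-16 and later outcome is 0.5 to 0.85;
- f is the share of the drug effect that switched placebo subjects have reached at the later visit.

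**Step 1: who switches.** Take improvement as normal. An EASI 75 rate of 50% puts the 420 mg mean at 75. A rate of 15% puts the placebo mean at 75 − 1.036s. The share below 50 is:
- placebo: Φ(1.036 − 25/s), which is 51% (s = 25) to 70% (s = 50), or about 28 to 38 of 54;
- 420 mg: Φ(−25/s), which is 16% to 31%, or about 9 to 17 of 54.

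**Step 2: week 16, before the switch.** The mean among failures is μ − sλ, where λ = φ(a)/Φ(a) and a = (50 − μ)/s.
- s = 25: λ is 0.775 (placebo) and 1.525 (420 mg). The means are 49.1 − 19.4 = 29.7 and 75 − 38.1 = 36.9, so 420 mg looks better by about 7 points.
- s = 50: λ is 0.491 and 1.141. The means are 23.2 − 24.5 = −1.4 (unrounded inputs) and 75 − 57.1 = 17.9, so 420 mg looks better by about 19 points.

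**Step 3: after the switch.** The 420 mg minus placebo difference in improvement is D = (1 − f) × 1.036s − r × s × (λ for 420 mg − λ for placebo). For example, with s = 50 and r = 0.7:
- f = 1: 0 − 22.8 = −22.8;
- f = 0.5: 25.9 − 22.8 = +3.1;
- f = 0.25: 38.9 − 22.8 = +16.1.

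D = 0 at f = 1 − 22.8/51.8 = 0.56. Over the assumed ranges the crossing point is about 0.4 to 0.7.

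**Step 4: EASI points.** A simulation used a log-normal EASI ratio (log SD 0.8 or 1.1), baseline EASI of 16 plus a gamma variable (mean about 30), and regression of change from day 1 on arm and baseline at a single visit, as a stand-in for the MMRM contrast at that visit. Positive values favour 420 mg.

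| Time | f | D, points of % improvement | D, EASI points |
|---|---|---|---|
| Week 16 | – | +7 to +19 | +7 to +11 |
| Later | 0.25 | +3.5 to +22.6 | +3.5 to +9.3 |
| Later | 0.5 | −3 to +10 | −1.0 to +3.8 |
| Later | 1 | −9 to −28 | −4 to −11 |

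With 54 per arm and f = 1, 420 mg has the worse point estimate in 81 to 98% of simulated trials and is nominally significantly worse in 19 to 51%. With f = 0.5 it has the worse point estimate in 26 to 58%. In one setting (f = 1, r = 0.7, log SD 1.1), doses with true EASI 75 rates of 15%, 25%, 35% and 50% look worse than placebo by 0.0, 2.2, 4.6 and 8.3 EASI points. There, the better the dose, the worse it looks.

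**Step 5: would a switch-date reference solve it?** A separate simulation, on similar assumptions with all switchers at full effect at week 36, gave the 420-to-420 group a change from day 1 of −13 to −15 EASI points, of which 70 to 83% came before the switch. That leaves between 0.17 × 13 = 2.2 and 0.30 × 15 = 4.5 points of apparent gain with no change of regimen. This is regression to the mean, because subjects were selected on a poor week-16 value.

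**The case against.** The strongest reply is that little depends on this analysis. It is exploratory, its p-values are nominal, and the main long-term MMRM truncates data after the switch, so the Part A comparison of randomized arms is not contaminated. That stands, and it sets the priority.

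Second, the direction of the distortion is not fixed. Week 24 is only six weeks after the switch. Protocol 3.1 argues that 12 weeks of treatment may have been too short in the previous phase 2a study and that improvement may continue beyond week 16. Both points allow f to be well below 1 at the early visits. That stands too. A reader might infer that an effective dose is bound to look worse than placebo in this set. The documents do not support that: the contrast favours 420 mg before the switch, and it may do so afterwards if onset is slow.

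Third, the day-1 reference is defensible. It avoids measuring from the value used for selection, and with all observations in the model the week-16 and later LS means can be compared directly. A reader might infer that measuring from the switch is the cure. Step 5 shows that it brings its own bias.

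Fourth, some of the text is unavailable. SAP 6.6, which should define the Switcher Analysis Set, is not in the supplied text. Membership is inferred from Protocol 7.4 and SAP 5.1 and 5.2, and the reporting of differences is inferred from the word repeated. The v3.0 change summary mentions change from the switching date. The current 9.5.3.1 contains no such model, which is not counted as an error, but the sponsor may already have meant to include one.

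None of this turns the between-arm difference into a treatment effect.

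**Conclusion.** The point holds as a minor one. The post-switch between-arm differences mix selection on a treatment-affected outcome with the speed of response to a newly started dose, and neither is the effect of the randomized dose. The possible distortion is several EASI points in either direction. The variability, correlation, baseline distribution and f behind these figures are assumed; only the response rates, dropout and arm size are the plan's. Rescue is not modelled, although SAP 5.4 disregards scores from the date of TCS/TCI rescue onwards, so the switchers who contribute late data may differ from those simulated. The case for dropping the contrast does not depend on these figures, since it follows from the selection rule and the common regimen. A reader should not infer any effect on the type I error or on the primary conclusions.

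**What to change.** In SAP 9.5.3.1, for the Switcher Analysis Set:

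1. State that between-arm LS mean differences will not be produced, and report LS means with 95% CIs within each randomized arm by visit, including week 16.
2. If wanted, add within-arm change from the last value before the Switching Date, alongside change from day 1. State that it includes regression to the mean because subjects were selected on a poor week-16 value.
3. State that the 420-to-420 group, whose regimen does not change, gives an indication of change without a change of treatment.

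The cost is a few lines of SAP text and, for item 2, one derived reference value. No new data are needed, and the descriptive switcher summaries already planned by randomized arm stay as they are.
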